### **1.5.2 Background and demographic characteristics**

The following common background and demographic variables from **core** study will be analyzed for assessing the baseline comparability:

#### **Continuous variables:**

- Age (which is derived from date of birth and the screening assessment date)
- Height
- Weight
- Body mass index (BMI)

#### **Categorical variables:**

- Age categories (<65 years, 65 years and older, 75 years and older)
- Gender
- Race
- Ethnicity
- Smoking status

Psoriasis specific baseline characteristics and history of disease will be summarized as well: Baseline PASI score , baseline PASI (<=20, >20), baseline total BSA baseline IGA mod 2011 score (at least mild, moderate, severe), Severity of psoriasis, presence of psoriatic arthritis (yes, no), types of previous psoriasis therapies, time since diagnosis of psoriasis, time since diagnosis of psoriatic arthritis, previous exposure to biologic systemic psoriasis therapy, previous exposure to systemic psoriasis therapy, previous exposure to non-biologic systemic psoriasis therapy, previous failure to biologic systemic psoriasis therapy, previous failure to systemic psoriasis therapy, previous failure to non-biologic systemic psoriasis therapy.

Previous psoriasis therapy will be combined from previous psoriasis therapy recorded in CORE study and also concomitant medications entered in EXTENSION study which started on or prior to the inform consent date of CORE study. The ATC code is defined in PDS.

Body Mass Index (BMI) will be calculated using the following formula:

$$\text{BMI} = (\text{body weight in kilograms}) / (\text{height in meters})^2$$

For BMI, height and body weight used is the last value prior to randomization. If there is no weight recorded prior to taking of study drug, BMI will be missing.

Unless otherwise specified, summary statistics will be presented for continuous variables for each treatment group and for all subjects (total) in the FAS. The number and percentage of subjects in each category will be presented for categorical variables for each treatment group and all subjects (total) in the FAS.

Unless otherwise specified, analyses will be based on the FAS.

### **1.5.3 Medical history**

Any significant prior or active medical condition at the time of signing informed consent will be coded using the MedDRA dictionary. These medical conditions will be summarized by primary system organ class and preferred term. Psoriasis specific medical history will be summarized by treatment group. Previous treatments for psoriasis and whether or not response was achieved will be summarized by treatment group.

The medical history information combines the medical history data collected in CORE study and also data entered in AE domain in the extension study which started on or prior to screening

### **1.6 Study medication**

The analysis of study treatment data will be based on the safety set.

The number of planned and actual injection number will be summarized by yearly interval (analysis visit) for entire treatment period and treatment group AIN457 150 mg FI and AIN457 300 mg FI.

In case it cannot be identified from the data collected or assumed from the planned treatment whether an injection contained placebo or secukinumab, it will be assumed that the syringe contained secukinumab. For example this applies to the 150 mg secukinumab treatment group (in which subjects should receive both an active and a placebo injection) if only one injection is given. If the medication pack number is not available, it will be assumed that the secukinumab injection was applied. If this scenario occurs for subjects in the 300 mg treatment group when subjects should receive two identical injections, it will be assumed that they received secukinumab as planned.

The duration of exposure to study drug will be summarized by treatment group and yearly interval for entire treatment period.

Duration of exposure will be defined and summarized as follows:

For extension study period, duration of exposure will be defined as the time from first dose of study medication in extension 1 to the end of treatment period in extension 1 study; and for entire study period duration of exposure will be defined as the time from first dose of study medication in core study to the end of treatment period in extension 1 study. The end of treatment period will be defined as the last dose plus 84 days or last visit whichever occurs earlier. i.e., for subjects who discontinued or have their last visit earlier than last dose plus 84 days, the end of study treatment exposure will be the date of the last study visit in the corresponding treatment period.

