Epoch	The planned stage of the subjects' participation in the study. Each epoch serves a purpose in the study as a whole. Typical epochs are: determination of subject eligibility, wash-out of previous treatments, exposure of subject to treatment or to follow-up on subjects after treatment has ended.
Investigational drug	The drug whose properties are being tested in the study; this definition is consistent with US CFR 21 Section 312.3 and is synonymous with "investigational new drug" or "investigational medicinal product."
Investigational treatment	All investigational drug(s) whose properties are being tested in the study as well as their associated treatment controls. This includes any placebos, any active controls, as well as approved drugs used outside of their indication/approved dosage or tested in a fixed combination. Investigational treatment generally does not include other treatments administered as concomitant background therapy required or allowed by the protocol when used within approved indication/dosage
Medication number	A unique identifier on the label of each investigational/study drug package in studies that dispense medication using an IRT system
Subject Number	A number assigned to each patient who enrolls into the study
Part	A subdivision of a single protocol into major design components. These parts often are independent of each other and have different populations or objectives. For example, a single dose design, a multiple dose design that are combined into one protocol, or the same design with different patient populations in each part.
Period	A subdivision of a cross-over study
Premature patient withdrawal	Point/time when the patient exits from the study prior to the planned completion of all investigational/study treatment administration and all assessments (including follow-up)
Randomization number	A unique identifier assigned to each randomized patient, corresponding to a specific treatment arm assignment
Rebound	A subject experiences a rebound, if PASI increases to > 125% of baseline PASI, or if new pustular psoriasis, or new erythrodermic psoriasis, or more inflammatory psoriasis occurs within 8 weeks after the last dose of study treatment has been received.

Stop study participation	Point/time at which the patient came in for a final evaluation visit or when study/investigational treatment was discontinued whichever is later

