Retreatment at start of relapse regimen – “SoR” “start of relapse”: either 150 or 300 mg s.c. secukinumab in PFS: “Start of relapse” will be defined as a loss of $\geq 20\%$ of the maximum PASI gain achieved during the CAIN457A2304 or CAIN457A2304E1 study, compared to baseline of the CAIN457A2304 study, *and* a loss of PASI 75 response. Whenever a subject fulfills the start of relapse criteria, active secukinumab will be administered at their scheduled visits (i.e., every four weeks) until the subject is back to PASI 75 response, at which point in time they will start receiving placebo again. The dose administered in the treatment period of this extension study (secukinumab 150 mg or 300 mg in PFS) will be identical to the dose that these subjects received during the maintenance period of the CAIN457A2304 core study. If a subject does not fulfill the criteria of a start of relapse or is back to PASI 75 response after a start of relapse, they will receive placebo PFS injections (two injections per dose) to maintain the blind. This treatment regimen is applied every four weeks, from Week 52 up to and including Week 152.

At Week 156, patients from the maintenance period of the CAIN457A2304 core study will be unblinded and continue in the study on one of the treatment options in [Table 5-1](#) according to investigator judgment for their assigned treatment arm.

Table 5-1 Open-label treatment options starting at Week 156

Previous treatment arm through Week 152 (Unblinded at Week 156)	Treatment options, as decided by the investigator	New office visit frequency
Secukinumab 300 mg FI	Continue secukinumab 300 mg FI	Every 12-16 weeks
Secukinumab 300 mg SoR	Continue secukinumab 300 mg SoR for remainder of the study OR Switch to secukinumab 300 mg dosed every 4 weeks	Every 4 weeks Every 12-16 weeks
Secukinumab 150 mg FI	Continue secukinumab 150 mg FI OR Switch to secukinumab 300 mg dosed every 4 weeks	Every 12-16 weeks Every 12-16 weeks
Secukinumab 150 mg SoR	Continue secukinumab 150 mg SoR for remainder of the study OR Switch to secukinumab 300 mg dosed every 4 weeks	Every 4 weeks Every 12-16 weeks

Open-label treatment arm for subjects entering from the CAIN457A2307 core study

Secukinumab 300 mg s.c. in PFS regimen arm: Each subject to continue receiving two s.c. injections of 150 mg secukinumab in PFS every four weeks. Doses will be administered from Week 52 up to and including Week 256.

Overview of treatment schedule according to treatment arm

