The treatment details for each treatment arm for Week 52 through Week 152 are highlighted in [Table 5-2](#) below. The treatment details for each treatment assignment for Week 156 through Week 256 are highlighted in [Table 5-3](#) below.

Table 5-2 Overview of treatment between Week 52 and Week 152

Treatment arm	Double-blinded A2304 subjects: Week 52 to Week 152	Open-label A2307 subjects: Week 52 to Week 152
secukinumab 150 mg fixed interval	1 s.c. secukinumab 150 mg PFS injection + 1 s.c. PBO secukinumab PFS injection	N/A
secukinumab 300 mg fixed interval	2 s.c. secukinumab 150 mg PFS injections	2 s.c. secukinumab 150 mg PFS injections
secukinumab 150 mg at start of relapse	At start of relapse and until PASI 75 is regained: 1 s.c. secukinumab 150 mg PFS injection + 1 s.c. PBO secukinumab PFS injection	N/A
	Otherwise: 2 s.c. PBO secukinumab PFS injections	N/A
secukinumab 300 mg at start of relapse	At start of relapse and until PASI 75 is regained: 2 s.c. secukinumab 150 mg PFS injections	N/A
	Otherwise: 2 s.c. PBO secukinumab PFS injections	N/A

PBO = placebo; PFS=pre-filled syringe

Table 5-3 Overview of treatment between Week 156 and Week 256

Assigned treatment	Treatment delivered and frequency of office visits
secukinumab 150 mg fixed interval	1 s.c. secukinumab 150 mg PFS injection every four weeks Office visits required every 12-16 weeks
secukinumab 300 mg fixed interval/ every four weeks	2 s.c. secukinumab 150 mg PFS injections every four weeks Office visits required every 12-16 weeks
secukinumab 150 mg at start of relapse	1 s.c. secukinumab 150 mg PFS injection every four weeks upon meeting SoR criteria and until PASI 75 is regained; no treatment otherwise Office visits required every 4 weeks
secukinumab 300 mg at start of relapse	2 s.c. secukinumab 150 mg PFS injection every four weeks upon meeting SoR criteria and until PASI 75 is regained No treatment otherwise

Assigned treatment	Treatment delivered and frequency of office visits
	Office visits required every 4 weeks

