Note: any AIN457 300mg (including AIN457 150mg FI switch to AIN457 300mg FI, AIN457 300mg FI, AIN457 150mg SoR switch to AIN457 300mg FI, AIN457 300mg SoR, AIN457 300mg SoR switch to AIN457 300mg FI and AIN457 300mg OL); any AIN 150mg (including AIN457 150mg FI and AIN457 150mg SoR); Any AIN457 including all the groups above.

The following study periods will be considered for analysis:

- **Extension study period:** Week 52 post-dose to Week 268;
- **Entire study period:** Combination of Induction (in A2304 core) period + Maintenance (in A2304 and in A2307) period + Core follow-up period (consider only for subjects who enter E1 after core follow-up period) + Treatment period in E1 [Initial Randomization in A2304 core to week 268] (including follow-up period);
- **Entire treatment period:** Combination of Induction (in A2304 core) period + Maintenance (in A2304 and in A2307) period + Core follow-up period (consider only for subjects who enter E1 after core follow-up period) + Treatment period in E1 [Initial Randomization in A2304 core to week 260]
- **Follow-up 2 period:** after W268 visit to end of the study.

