**Duration of exposure (days)=min(End of study visit date, last dose date + 84 days) - first dose date + 1**

Duration of exposure (years) = duration of exposure (days) / 365.25

Duration of exposure (100-patient years) = duration of exposure (years) / 100

The analyses of duration of exposure described above will be done for the extension study period and for the entire study period.

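### Pooled 150 mg and 300 mg exposure includes start-of-relapse time more than 84 days after the last active injection, and no active-injection count is planned to show how much

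*SAP*

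**What the plan says.** **Treatment in the SoR arms.** Under Protocol 5.2, SoR subjects who are not in relapse, or who have regained PASI 75, are still injected every four weeks up to Week 152, but "they will receive placebo PFS injections (two injections per dose) to maintain the blind". Protocol Table 5-3 then gives SoR subjects active injections from Week 156 only "upon meeting SoR criteria and until PASI 75 is regained; no treatment otherwise".

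**Pools.** SAP 1.2 defines "any AIN 150mg (including AIN457 150mg FI and AIN457 150mg SoR"). The 300 mg pool lists, among its components, "AIN457 300mg SoR, AIN457 300mg SoR switch to AIN457 300mg FI and AIN457 300mg OL". SAP Table 1-2 marks duration of exposure and the safety analysis for both pools. It also marks them for each fixed-interval (FI), SoR and open-label (OL) group separately.

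**Exposure.** SAP 1.6 sets duration in days as "min(End of study visit date, last dose date + 84 days) - first dose date + 1". The incidence-rate denominators in SAP 1.9.1 and 2.4.1 use the same last-dose-plus-84-days limit. None of these sections subtracts time between active courses.

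**Injection counts.** SAP 1.6 plans planned and actual injection numbers by year "for entire treatment period and treatment group AIN457 150 mg FI and AIN457 300 mg FI". No active-injection count for the SoR arms is planned anywhere.

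**What a dose is.** The protocol glossary includes "any placebos, any active controls" under investigational treatment. Protocol 5.5.4 lists a placebo dose for SoR subjects and counts placebo syringes as study treatment injections. The SAP does not say whether first and last dose mean active doses.

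**The concern.** Long-term safety is the primary objective, and the two pools are the columns a reader would take as the safety record at each dose. A SoR subject carries the dose label of the randomised arm throughout, although long stretches may contain no secukinumab.

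Two things follow. Total exposure in the pooled and SoR columns is larger than time on drug. Exposure-adjusted rates in those columns also fall for events that occur less often off drug, because drug-free person-time enters the denominator along with the few events that arise in it.

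The injection table that would let a reader judge this covers only the FI arms, where the number of active injections hardly varies. It omits the arms where it can vary from 0 to 26 dosing visits between Week 52 and Week 152.

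**Working it through.** **1. The plan's own figures (Protocol 9.7).** 918 × 0.95 × 0.85 = 741, against about 740 stated. 740 × 0.80 / 4 = 148 per arm, as stated. 1 − 0.999^148 = 13.8% and 1 − 0.99^148 = 77.4%, against 14% and 77%. These reproduce, so 148 per arm is used below.

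**2. One subject under the exposure formula.** SAP Table 1-8 gives Week 52 = Day 365, Week 152 = Day 1065, Week 256 = Day 1793 and Week 268 = Day 1877. The visit-date limit is assumed not to bind before the dose limit.

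- *Placebo only from Week 52 to Week 152 and no injection afterwards, placebo counted as a dose:* 1065 + 84 − 365 + 1 = 785 extension days (785 / 365.25 = 2.15 years), with no active injection.
- *Same subject over the entire study:* 1065 + 84 − 1 + 1 = 1149 days. If the last active dose was at Week 8 (Day 57, assumed), the 84-day window closes on Day 141, and 1149 − 141 = 1008 days (88%) lie beyond it.
- *Only active extension dose at Week 256, placebo counted as a dose:* 1793 + 84 = 1877, and 1877 − 365 + 1 = 1513 days, the same as an FI completer.
- *Dose read as active only:* the first subject has no first extension dose, so extension exposure is undefined, and entire-study exposure falls from 1149 to 141 days. Gaps between two active courses are still counted.

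**3. How much of a relapse cycle is beyond 84 days.** For k active doses followed by m placebo visits, cycle length is 28(k + m) days and time beyond 84 days is max(0, 28(m + 1) − 84). For k = 1 to 3:

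- m = 1 or 2: 0%
- m = 3: 28/168 to 28/112 = 17% to 25%
- m = 6: 112/252 to 112/196 = 44% to 57%
- m = 12: 280/420 to 280/364 = 67% to 77%

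**4. SoR share of each pool before Week 156 (w).** This assumes equal person-time per subject. Any 150 mg: 148/296 = 1/2. Any 300 mg: OL is at most 740 − 4 × 148 = 148, giving 148/444 = 1/3. That remainder includes Week 12 non-responders, whom Protocol 1.1 takes off treatment, so the true OL number is smaller. With no OL subjects the share would be 148/296 = 1/2. So w at 300 mg lies between 1/3 and 1/2.

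**5. Effect on exposure and rates.** Let d be the share of SoR person-time more than 84 days after an active injection, and r the off-drug to on-drug event-rate ratio. Neither is in the documents, so both are assumed. If the on-drug rate is the same in all pooled arms:

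pooled rate / on-drug rate = 1 − w·d·(1 − r), and credited time / time on drug = 1 / (1 − w·d).

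| d | Any 150 mg (w = 1/2): rate ratio at r = 0.5; r = 0 | time factor | Any 300 mg (w = 1/3): rate ratio at r = 0.5; r = 0 | time factor |
|---|---|---|---|---|
| 0.25 | 0.94; 0.88 | 1.14 | 0.96; 0.92 | 1.09 |
| 0.50 | 0.88; 0.75 | 1.33 | 0.92; 0.83 | 1.20 |
| 0.75 | 0.81; 0.63 | 1.60 | 0.88; 0.75 | 1.33 |

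At r = 1 the rate ratio is 1.00 throughout, and only exposure is overstated. If w at 300 mg were 1/2, its columns would equal those for 150 mg. Induction, when every arm received active drug, lowers d in the entire-treatment-period analysis.

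**The case against.** **The groups are already shown apart.** Table 1-2 gives FI, SoR and OL their own exposure and safety columns, and the yearly adverse-event analyses in SAP 1.9.1 are for the FI cohorts. A reader might infer that all dose-labelled safety rates are diluted and that nobody could tell. The documents do not support that: FI and OL columns contain no SoR time. This part of the objection stands and limits the point to the pooled and SoR columns. It does not remove it, because Table 1-2 marks the safety analysis for the pools and SAP 1.9.1 applies a rate threshold of 5.0 per 100 subject-years to them.

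**Not all placebo time is drug-free.** By the SAP's own rule, time within 84 days of an active injection is on treatment, and short placebo gaps add nothing. This stands. Only the longer gaps matter.

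**Dose may mean active dose.** SAP 1.8.1 treats the absence of a dosing record at Weeks 92 and 144 as no active treatment given, which points that way. Protocol 5.5.4 points the other way. The wording is ambiguous, so the 785 days are conditional, and they are an extreme case in any event. The formula also stops credit 84 days after the last injection, so untreated time trailing on after Week 156 is not counted. The active-only reading still leaves gaps between active courses in the denominator.

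**Dose comparison.** A reader might infer that 150 mg looks safer relative to 300 mg because SoR is a larger part of its pool. At d = r = 0.5 the two ratios differ by about 5% (0.875 / 0.917 = 0.95), but that needs all 148 remaining subjects to be OL. With fewer, the gap shrinks and could be near zero. SAP 1.8.3 plans no formal testing. This objection stands.

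**Regimen.** Placebo intervals belong to the SoR regimen, and pooling by assigned dose is a legitimate presentation. That argues for keeping the pools. It does not justify leaving active drug uncounted in the SoR arms.

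**Conclusion.** The point holds in limited form. As written, SAP 1.2, 1.6, 1.9.1 and 2.4 count SoR intervals more than 84 days after the last active injection as exposure at the labelled dose. This overstates time on drug in Any 150 mg, Any 300 mg and the SoR columns, and lowers exposure-adjusted rates there for events less frequent off drug. FI and OL columns and the yearly FI analyses are sound in this respect.

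No single size can be given. The active share of SoR time is not in the documents, and no planned table would reveal it. Over the assumed range d = 0.25 to 0.75 and r = 0 to 1, the pooled rate is 0.63 to 1.00 of the on-drug rate at 150 mg, and 0.75 to 1.00 at 300 mg if w = 1/3. These figures rest on planned arm sizes, equal person-time, a common on-drug rate and the period before switching at Week 156. A distortion of the comparison between doses is not established.

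**What to change.** 1. In SAP 1.6, extend the injection summary to 150 mg SoR and 300 mg SoR, counting active injections only, identified from IRT kit type.
2. In SAP 1.4.6, 1.6, 1.9.1 and 2.4.1, state whether first and last dose mean active dose, and how a subject with no active extension dose is handled.
3. Keep the planned pools, and add exposure and exposure-adjusted rates for Any 150 mg and Any 300 mg without SoR. An alternative second version keeps SoR but limits its events and person-time to within 84 days of an active injection.

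Replacing the pools outright is a matter of preference and is not needed.

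The cost is SAP wording and a few extra columns. Protocol 8.3 says the IRT tracks the drug dispensed, so no new data are needed and trial conduct does not change. Intervals in the pools without SoR will be wider, but the planned pools remain beside them.

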**Duration of exposure (days)=min(End of study visit date, last dose date + 84 days) - first dose date + 1**

Duration of exposure (years) = duration of exposure (days) / 365.25

Duration of exposure (100-patient years) = duration of exposure (years) / 100

The analyses of duration of exposure described above will be done for the extension study period and for the entire study period.

## **1.7 Concomitant medication**

Medications will be identified using the Novartis Drug and Therapy Dictionary (NovDTD) including Anatomical Therapeutic Chemical (ATC) code. Prior and concomitant treatments will be summarized by treatment group for the safety set.

Prior and concomitant medications will be summarized by treatment group in separate tables. Medications will be presented in alphabetical order, by ATC codes and grouped by *anatomical main group* (the 1st level of the ATC codes). Tables will also show the overall number and percentage of subjects receiving at least one drug of a particular ATC code and at least one drug in a particular anatomical main group.

Prior medications are defined as drugs taken and stopped prior to first dose of study treatment. Any medication given at least once between the day of first dose of randomized study treatment, and last dose plus 84 days or last visit (including follow-up visits) whichever occurs earlier will be a **concomitant** medication, including those which were started pre-baseline and continued into the treatment period.

In addition, medical procedures and significant non-drug therapies as coded in MedDRA will be summarized.

Prior or concomitant medication will be identified based on recorded or imputed start and end dates of medication taken. Further rules will be given in [PDS](#).

Listings of prior or concomitant medication during entire study period and follow-up 2 period will be provided separately.

